3.8.1 Adverse Events

AEs will be coded using the MedDRA dictionary (Version 20.1 or higher). Treatment-emergent AEs (TEAEs) are any AE occurring or worsening in severity after the first administration of study medication. All AEs (including SAEs) will be graded using the 5-point Common Terminology Criteria for Adverse Events (CTCAE) V5.0 scale (mild, moderate, severe, life-threatening, or death). Causality with KD019 will be classified as: definitely related; probably related; possibly related; unlikely related; unrelated; or not related.

The number and percentage of patients who experienced at least one TEAE as well as the number and percentage of patients who experienced AEs of each specific SOC and PT will be presented. For the presentation of AE incidences, the SOCs and the PTs within each SOC will be presented by decreasing total frequency. Tabulation by maximum severity and relationship to tesevatinib will also be included by treatment group.

The TEAEs, Grade ≥ 3 TEAEs, SAEs, and TEAEs leading to dose modification/discontinuation will be summarized by treatment arm, SOC, and PT. These analyses will be repeated for events considered related (definitely related/probably related/possibly related) to tesevatinib.

Subject listings will be provided for SAEs, AEs resulting in study drug discontinuation and deaths.

Adverse events will also be presented in listings. Time to onset and duration of AEs will be included in listings, along with action taken and outcome.

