Duration of Treatment	Subjects will receive study drug for 28 days after the initiation of treatment. After the initial 28-day safety and tolerability assessment period, subjects will, at the investigator's discretion, continue to receive study drug for a total of 24 months from the initiation of treatment. Subjects will be followed for a period of 30 days following the last dose of tesevatinib.
Concomitant Medications	Subjects should avoid ingesting grapefruit, pomelo, or Seville fruit (and juice) with tesevatinib or at any time during the study. Subjects should not take medications that are associated with a risk of QTc(F) interval prolongation and/or torsades de pointes. Additionally, subjects are not permitted to take concomitant medications that inhibit the CYP3A4 isozyme (eg, ketoconazole, itraconazole, erythromycin, clarithromycin) or inducers (eg, dexamethasone, phenytoin, carbamazepine, rifampicin, or phenobarbital). Tesevatinib is also highly protein bound, and other drugs that are also highly protein bound with the exception of warfarin (eg, diazepam, furosemide, dicloxacillin, propranolol, and phenytoin) should be avoided.
	Antiemetics and antidiarrheal medications should not be administered prophylactically before initial treatment with study drug. At the discretion of the investigator, treatment of symptoms with antiemetic and antidiarrheal medications may be undertaken per standard clinical practice.
	Since tesevatinib is a potent inhibitor of MATE transporter proteins, increased levels of concomitant medications that are secreted by the kidney proximal tubule cells into the renal tubule by MATE transporter proteins may occur. Thus, subjects taking cephalexin, cimetidine, dofetilide, fexofenadine, metformin, procainamide, and pyrimethamine should be monitored carefully.
Safety Assessments	Safety assessments will be performed at regular study intervals (refer to Study Assessment table) and include AEs, physical examinations, vital sign measurements, clinical laboratory evaluations (especially renal function), ECGs, echocardiograms, concomitant medication, and pregnancy testing.
	The AE reporting period for a subject enrolled in the study will begin after informed consent through 30 days after the last dose of tesevatinib. Clinical laboratory tests (hematology, chemistry, urinalysis, coagulation,

and thyroid-stimulating hormone [TSH]) will include the following:

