- Evaluate the annualized percent change from baseline in total kidney volume (TKV). TKV will be determined by MRI at Screening (baseline measurement), at the 6-month visit, and every 6 months thereafter.

Statistical Methods

Eight subjects per cohort are standard and a reasonable sample size for determination of safety and tolerability in this Phase 1b/2a study. In the Phase 2a cohort, 24 subjects were enrolled at the MTD using alternative dosing schedules of 150 mg of tesevatinib on Monday, Wednesday, and Friday of each week, or 150 mg of tesevatinib on Monday and Thursday of each week. There were 15 additional subjects in the Phase 2a cohort dosed at 50 mg of tesevatinib daily and up to 50 additional subjects are planned. These subjects who receive 50 mg daily of tesevatinib will provide 75% likelihood of having at least 1 AE if the true incidence of an AE is 5%.

Demographic (eg, gender, age, race) and baseline characteristics (height, weight) will be summarized by dose level and cohort.

Safety analyses will be performed on all subjects who receive any quantity of tesevatinib. Data generated from safety assessments will be presented in listings by subject and summarized by treatment cohort with the Phase 2a cohort being analyzed separately. Treatment-emergent AEs will be summarized using version 18.1 or higher of MedDRA System Organ Class (SOC) and preferred term, classified from verbatim terms. The incidence and percentage of subjects with at least 1 occurrence of a preferred term will be included, according to the most severe intensity. The number of events per preferred term will also be summarized.

Causality (relationship to study treatment) will be summarized separately. ECG (QT/QTc[F]) and PK data will be provided in a prospective statistical plan that will detail the statistical method of analyzing the ECG data and morphological findings.

Efficacy will be explored with regard to the effect of tesevatinib on eGFR. In the Phase 2a cohort, the 65 subjects in the 50 mg QD dose group will allow an 80% confidence interval of approximately \pm 0.64 mL/min about an expected mean 6-month change from baseline of -2.5 mL/min when the standard deviation is 4.0 mL/min. Additional statistical details will be provided in a prospective statistical plan.

Table 4-1: Schedule of Events for Subjects Enrolled in the Safety in Larger Kidneys (SILK) 50 mg Daily Portion of the Study

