5.2.2.2.3 Initial Data from ADPKD Protocol KD019-101

Sixty-one subjects were enrolled into 5 dosing cohorts in the Phase 1b and Phase 2a portions of the study: 9 subjects into Cohort 1 at 50 mg daily, 8 subjects into Cohort 2 at 100 mg daily, 5 subjects into Cohort 3 at 150 mg daily, 14 subjects into Cohort 4 at 150 mg Monday, Wednesday, and Friday, 10 subjects into Cohort 5 at 150 mg Monday and Thursday, and an additional 15 Phase 2a subjects at 50 mg daily (Table 5-1).

Table 5-1: Summary of KD019-101 Dose / Schedule, Demographics and Median TKV (mL)

	Gender (Male [M]/Female [F])	Median Age (Years)	Median TKV (mL)	
24	9M / 15F	39	1401*	
8	5M / 3 F	37	1525	
5	2M / 3 F	41	1094	
14	4M / 10 F	36	1344	
10	4M / 6 F	37	795	
61	24M / 37F	38 (19-55)	1333.5* (411-4432)	
	8 5 14 10	8 5M/3 F 5 2M/3 F 14 4M/10 F 10 4M/6 F	8 5M/3F 37 5 2M/3F 41 14 4M/10F 36 10 4M/6F 37	

Safety reviews after the first 2 cohorts deemed these cohorts to have adequate safety and to be tolerable. In Cohort 3, 3 of 5 subjects enrolled have withdrawn consent primarily due to concerns with rash. It was noted that all 5 subjects in this cohort experienced rash within the first 28 days of treatment. In comparison, 4 out of 9 subjects in the 50-mg cohort and 1 out of 8 subjects in the 100-mg cohort experienced rash within the first 28 days. While rash at the 150 mg dose level did not meet strict safety criteria for defining the MTD, this dose level was considered intolerable for long-term administration in this population. Therefore, the MTD for daily dosing was determined to be 100 mg daily. While the MTD dose of 100 mg/day was based on criteria defined in the protocol, the occurrence of moderate QTc prolongation in 2 subjects dosed at that level led to a decision later in the study to recommend 50 mg/day as the best tolerated daily dose.

As the known toxicities of tesevatinib, including diarrhea and rash, have been seen in all 3 Phase 1b dosing cohorts, an alternative dosing schedule of dosing 150 mg of KD019 on Monday,

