14.3.8 Safety Data

Safety analyses will be performed on all subjects who receive any quantity of study drug. AEs that are unrelated to treatment and that occur more than 30 days after the administration of the last dose of treatment will not be reported or analyzed. Safety evaluation will be performed based on the actual study treatment a subject has received. A separate set of safety analyses will be presented for the Phase 2a cohort.

Safety observations and measurements include AEs, safety laboratory tests, vital sign measurements, physical examinations, pregnancy status, echocardiograms, ECG assessments, and pharmacokinetic data.

Adverse events will be summarized both overall and by dose cohort and tabulated by severity and relationship to tesevatinib (causality). The original terms used by investigators to identify adverse events in the eCRFs will be mapped into preferred terms using MedDRA® (Version 18.1 or higher). Adverse events will then be grouped by MedDRA® preferred terms into frequency tables according to body system. The number and percentage of subjects experiencing adverse events will be tabulated by body system and preferred term both overall and by dose cohort. When an adverse event occurs more than once, the maximum severity and causality will be counted. Additionally, serious adverse events, adverse events that are related to tesevatinib, and adverse events that are unrelated to tesevatinib will be summarized separately. Concurrent illnesses will be listed and examined as possible confounders in the treatment relationship. Finally, any other potentially related adverse events will be analyzed and discussed, as necessary. Concurrent medications/therapies will also be listed.

A listing of all AEs and SAEs by subject will also be provided. The duration of AEs will be determined and included in listings, along with action taken and outcome. Incidence of laboratory abnormalities will be summarized. The worst on-study grade after the first dose of study drug will be summarized. The incidence of NCI-CTCAE Grade ≥ 3 (Version 4.03) laboratory abnormalities under treatment and shifts in toxicity grading from baseline to highest grade post-baseline will be displayed. Results for variables that are not part of the NCI CTCAE (Version 4.03) will be presented in the listings as below, within, and above the normal limits of the local laboratory. Pregnancy test results will be summarized by time point and dose cohort.

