3.1.3.2 Binary Endpoint and Other Categorical Variables

For endpoints with two possible outcomes such as alive/otherwise or response/otherwise within specific periods, the 95% confidence interval will be calculated with Clopper-Pearson method for survival rates or response rates. For other categorical variables, the counts and percent of each category within a parameter will be calculated for observed data only. The denominator for all percentages, unless otherwise specified, will be the number of subjects in the cohort or in the specified analysis population.

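### AE tables give crude percentages by cohort over unequal follow-up, so events that accrue with time on drug cannot be compared across cohorts; a Days 1-28 table by cohort is a cheap remedy

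*SAP*

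**What the plan says.** **Measure.** SAP 3.8.1 gives "The number and percentage of patients who experienced at least one TEAE", with the same form for system organ classes and preferred terms, Grade 3 or higher events, serious events, and events leading to dose modification or discontinuation. Protocol 14.3.8 agrees: "The number and percentage of subjects experiencing adverse events will be tabulated by body system and preferred term both overall and by dose cohort". The protocol synopsis (Statistical Methods) adds counts: "The number of events per preferred term will also be summarized". No exposure denominator goes with those counts.

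**Denominator.** Under SAP 3.1.3.2 the default for percentages "will be the number of subjects in the cohort or in the specified analysis population". It is a number of people, not time at risk.

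**Window.** SAP 3.8.1: "Treatment-emergent AEs (TEAEs) are any AE occurring or worsening in severity after the first administration of study medication". This has a start but no stated end. The protocol collects AEs to 30 days after the last dose (13.2).

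**Follow-up.** One dose qualifies a subject for the Safety Population (SAP 3.2). After the initial 28 days, at the investigator's discretion, subjects "continue to receive study drug for a total of 24 months from the initiation of treatment" (Protocol synopsis, Duration of Treatment; also 11.1).

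**What else falls inside that time.** Active Phase 1b subjects were moved to 100 mg daily (Protocol 7.2, 11.2), and SILK subjects have a 28-day holiday after their first 28 days (9.2.3). Protocol 14.3.8 evaluates safety by treatment actually received. The SAP does not say how time and events after a switch are assigned.

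**Timing information kept.** Time to onset appears in listings (SAP 3.8.1) and exposure in a separate Table 14.2.1. Neither document plans final AE tables on a common window, an AE rate per time at risk, or a cumulative incidence.

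**The concern.** The proportion of subjects ever affected rises with time on study even when the underlying risk is unchanged. If cohorts differ in how long subjects stay, their percentages differ for that reason alone.

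The documents show that length of stay did differ: "In Cohort 3, 3 of 5 subjects enrolled have withdrawn consent primarily due to concerns with rash" (Protocol 5.2.2.2.3). Time at the assigned dose also differs by design, through the move of Phase 1b subjects to 100 mg daily and through the SILK holiday.

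Tolerability of the two alternative schedules is a secondary objective (SAP 2.1.2.1), so readers will set the cohort columns side by side. Protocol 5.2.2.2.3 already does so in two ways. For rash it uses a fixed window, as in "1 out of 8 subjects in the 100-mg cohort experienced rash within the first 28 days". For QTc(F) prolongation it contrasts one moderate case among 14 Monday/Wednesday/Friday subjects with none to date among 10 Monday/Thursday subjects, and states no follow-up time for either. The SAP keeps the second habit and drops the first.

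**Working it through.** **Plan's own figure.** The only AE calculation in the plan is a 75% chance of at least one AE at 5% incidence (Protocol 14.2, SAP 3.1.2). It names no time window. From 1 - 0.95^n, n = 8 gives 33.7%, n = 24 gives 70.8% and n = 65 gives 96.4%; 75% needs n of about 27. That mismatch is a separate matter, and nothing below depends on it.

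**Inputs for the illustration.** The range of follow-up, one 28-day cycle to about 24 months (26 cycles), is from the documents. Event risk per cycle and actual exposure by cohort are not given. I assume a constant first-event risk p of 1%, 2% or 5% per 28 days.

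**Step 1: same risk, different follow-up.** Crude percentage = 1 - (1 - p)^k after k cycles.

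| p per 28 days | k = 1 | k = 6 | k = 26 |
|---|---|---|---|
| 1% | 1.0% | 5.9% | 23.0% |
| 2% | 2.0% | 11.4% | 40.9% |
| 5% | 5.0% | 26.5% | 73.6% |

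The risk within each row is identical; only follow-up changes. The end columns are extremes (everyone stops at Day 28, or everyone completes), and no cohort is documented at either.

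**Step 2: partial early exit.** Suppose 60% leave at Day 28 (the 3/5 fraction from Cohort 3; the day is assumed) and the rest stay 26 cycles. At p = 2% the crude figure is 0.6 x 2.0 + 0.4 x 40.9 = 17.6%, against 40.9% if all stay.

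**Step 3: can the order reverse?** A regimen with twice the hazard of p = 2%, followed for 6 cycles, shows 1 - 0.98^(2 x 6) = 21.5%. The regimen with the lower hazard, followed for 26 cycles, shows 40.9%. Under constant hazard the order reverses whenever the riskier regimen is followed for less than half as long.

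**Step 4: events that cause the exit.** These are already counted. First-28-day rash in Protocol 5.2.2.2.3, with Clopper-Pearson 95% intervals:

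| Cohort | Rash | % (95% CI) |
|---|---|---|
| 50 mg daily | 4/9 | 44.4 (13.7 to 78.8) |
| 100 mg daily | 1/8 | 12.5 (0.3 to 52.7) |
| 150 mg daily | 5/5 | 100 (47.8 to 100) |

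Early departure at 150 mg daily does not lower its rash percentage.

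**Step 5: does a simple person-time rate solve it?** Not for early events. Take 4 of 9 subjects with rash, all at an assumed Day 14, and the other 5 at risk to last dose + 30 days.

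- Stop at Day 28: 4 x 14 + 5 x 58 = 346 days; 4/346 x 365.25 = 4.2 per subject-year.
- Stay 730 days: 4 x 14 + 5 x 760 = 3,856 days; 4/3,856 x 365.25 = 0.38 per subject-year.

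The early risk is identical, yet the rates differ 11-fold. The assumption that fails is constant hazard: Protocol 11.3.2.1 describes acneiform rash as arising in the first few weeks and peaking at Weeks 4-6.

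**Step 6: why Days 1-28 works.** The window ends before the SILK holiday begins, and before the optional 50 to 100 mg escalation, which required at least 6 months. AE collection to 30 days after the last dose means it is largely observed even in subjects who stop early. It is near-common in the intermittent cohorts too, whose initial period is 25 or 26 days (Protocol 11.1).

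**The case against.** The strongest reply is that this is a descriptive report on small, sequential, nonrandomized cohorts. No between-cohort AE test is planned, SILK enrols a different population, and adjusting for time would not make the cohorts comparable. All cohorts share the same nominal 24 months. QTcF categories and laboratory values are already tabulated by visit (SAP 3.8.2, 3.8.4), which gives those two domains a common time axis. The discontinuation tables, exposure table and onset listings show part of the picture. All of this stands. It limits the harm to misreading, but it does not supply an AE table in which cohorts are seen over the same period.

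Three stronger readings are tempting, and the documents do not support them.

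- *Regimens that subjects leave early will look safer.* The one documented case runs the other way: rash at 150 mg daily is 5/5. The distortion applies to later-accruing events that are not the reason for leaving; late pericardial or ocular findings are possible examples.
- *The choice of regimen rests on these tables.* SAP section 1 states that 50 mg daily had already been selected, and escalation was decided on reviews of at least 28 days of data.
- *Cohorts will differ by tens of percentage points.* That follows only from the assumed extremes in Step 1.

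The objection to replacing crude percentages with a person-time rate across the board is also right, as Step 5 shows.

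**Conclusion.** The point holds in a limited form. As planned, AE percentages by cohort combine event risk with unequal follow-up and, for Phase 1b and SILK, with dose changes or time off drug. This affects events that accrue over time and do not cause exit; early events such as rash at 150 mg daily are not understated.

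The size of the bias cannot be derived, because neither document gives exposure by cohort or AE hazards. The figures in Steps 1 to 3 show the mechanism under an assumed constant risk and are not estimates for this trial.

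The consequence is possible misreading of the descriptive tables that serve the secondary tolerability objective. No test result and no regimen decision is invalidated. I would call the remedy a cheap improvement.

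**What to change.** In SAP 3.8.1 and the table list in section 4:

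1. Keep the crude tables, labelled as covering all follow-up, and state where the TEAE window ends.
2. Add a by-cohort table of subjects with each TEAE, related TEAE and Grade 3 or higher TEAE with onset in Days 1-28. Footnote the 25- or 26-day initial period of the intermittent cohorts and any subject whose dose changed or who was lost within the window. Use this table when tolerability is described across cohorts.
3. For later-accruing events, add cumulative incidence by time since first dose, or an exposure-adjusted rate. Assign time and events to the dose actually received, in line with Protocol 14.3.8, and state whether the SILK holiday counts as time at risk.
4. State that a constant-hazard rate will not be used for early-onset events such as rash.

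**Cost.** SAP wording and a few extra tables from onset and dosing dates already recorded; no new visits or data. The downsides are imprecise estimates in cohorts as small as 5 to 14 subjects and the need to settle the rule for time after dose switches.

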Wednesday, and Friday of each week was explored in the Phase 2a portion of the study to determine if it is more tolerable when used chronically in this subject population. The safety data of the 14 subjects who received 150 mg tesevatinib every Monday, Wednesday and Friday has been reviewed by the Data Safety Committee. There were 3 moderate events: 1 subject had moderate QTc(F) prolongation which resolved with dose modification as well as moderate diarrhea, and 1 subject with moderate rash which improved with topical corticosteroids and emollients. While the tolerability of this schedule appears to be superior to that of dosing tesevatinib 150 mg on a daily schedule, another dosing schedule of tesevatinib 150 mg administered on Monday and Thursday of each week was explored to determine if this dose and schedule would result in fewer moderate toxicities, particularly QTc(F) prolongation. To date, of the 10 subjects receiving 150 mg Monday and Thursday, there was no QTc(F) prolongation; however, 1 subject had a severe (Grade 3) maculopapular skin rash. Thus, while the 150 mg Monday and Thursday administration of tesevatinib generally appears to be a tolerable regimen, the occurrence of the Grade 3 maculopapular skin rash, together with the significant effect of missing any single dose in this regimen, has led to the decision to further evaluate the dose level of 50 mg daily prior to using this dose in a randomized study.

Following the enrollment of the additional 15 subjects in the Phase 2 50 mg dosing cohort, it was concluded that tesevatinib 150 mg in various schedules was associated with skin rash that was not well tolerated. Incidence of moderate QTc prolongation not acceptable for chronic use was associated with tesevatinib 100 mg daily. Tesevatinib 50 mg daily appeared to be a well-tolerated dose in patients with ADPKD, although some acneiform rash occurred. The study will enroll approximately 50 more subjects at the dose of 50 mg daily in order to increase the robustness of the safety data in subjects with ADPKD treated with tesevatinib.

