4 LIST OF TABLES, FIGURES, AND LISTINGS

In all tables, figures and listing, results will be presented by treatment cohorts and overall, unless be otherwise specified.

Table/Listing/Figure	Title
Demographics and Baseline Characteristics	
Tables (14.1.Y.Z)	Table 14.1.1 Screen Failure
	Table 14.1.2 Patient Disposition
	Table 14.1.3 Summary of Demographics and Baseline Characteristics
	Table 14.1.4 Summary of Major Protocol Deviations
	Table 14.1.5 Summary of Medical History
Treatment Exposure and Concomitant Medication	
Tables (14.2.Y.Z)	Table 14.2.1 Summary of Treatment Compliance and Exposure
	Table 14.2.2.a Summary of Prior Medications
	Table 14.2.2.b Summary of Concomitant Medications
Efficacy	
Tables (14.3.Y.Z)	Table 14.3.1 Annualized Change in Estimated Glomerular Filtration Rate
	Table 14.3.2 Annualized Percent Change from Baseline in Height Adjusted Total Kidney Volume
	Table 14.3.3 Annualized Percent Change from Baseline in Reciprocal of Serum Creatinine

	Table 14.3.3.1 Annualized Percent Change from Baseline in Reciprocal of Serum Creatinine for Study 101
Safety	
Tables (14.4.Y.Z)	Table 14.4.1 Summary of AEs
	Table 14.4.1.1 Summary of AEs for Study 101
	[REDACTED]
	Table 14.4.2 Summary of TEAEs
	Table 14.4.2.1 Summary of TEAEs for Study 101
	[REDACTED]
	Table 14.4.3 Summary of TEAEs Related to KD019
	Table 14.4.3.1 Summary of TEAEs Related to KD019 for Study 101
	[REDACTED]
	Table 14.4.4 AEs by Preferred Term and Maximum Severity
	Table 14.4.4.1 AEs by Preferred Term and Maximum Severity for Study 101
	[REDACTED]
	Table 14.4.5 AEs by Preferred Term and Strongest Relationship
	Table 14.4.5.1 AEs by Preferred Term and Strongest Relationship for Study 101
	[REDACTED]
	Table 14.4.6 Summary of Grade ≥ 3 TEAEs by System Organ Class and Preferred Term
	Table 14.4.6.1 Summary of Grade ≥ 3 TEAEs by System Organ Class and Preferred Term for Study 101
	[REDACTED]
	Table 14.4.7 Summary of Grade ≥ 3 TEAEs Related to KD019 by System Organ Class and Preferred Term

	Table 14.4.8 Summary of Serious Adverse Events
	Table 14.4.9 Summary of Serious Adverse Events Related to KD019
	Table 14.4.10 Summary of TEAEs leading to Dose Modification
	Table 14.4.11 Summary of TEAEs Related to KD019 leading to Dose Modification
	Table 14.4.12 Summary of TEAEs leading to Dose Discontinuation
	Table 14.4.13 Summary of TEAEs Related to KD019 leading to Dose Discontinuation
	Table 14.4.14 Summary of Clinical Laboratory: Hematology

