	Table 14.4.15 Summary of Clinical Laboratory: Chemistry
	Table 14.4.16 Summary of Clinical Laboratory: Any Other Clinical Labs
	Table 14.4.17 Shifts from Baseline for Hematology Assessment
	Table 14.4.18 Shifts from Baseline for Chemistry Assessment
	Table 14.4.19 Summary of Vital Sign Results and Change from Baseline
	Table 14.4.20 Summary of 12-Lead ECG and Change from Baseline
	Table 14.4.21 Summary of QTcF Interval Results
	Table 14.4.22 Overall Summary of AEs
	Table 14.4.23 Overall Summary of AEs for Study 101
	[REDACTED]
Listings (16.2.Y.Z)	Listing 16.2.1 Disposition of Subjects
	Listing 16.2.2 Protocol Deviations
	Listing 16.2.3 Patients Excluded From Efficacy Analysis
	Listing 16.2.4 Patient Demographics
	Listing 16.2.5 Dose Changes
	Listing 16.2.6.1 Estimated Glomerular Filtration Rate

	Listing 16.2.6.2 Height Adjusted Total Kidney Volume
	Listing 16.2.7.1 Adverse Events
	Listing 16.2.7.2 Adverse Events leading to Study Drug Discontinuation
	Listing 16.2.7.3 Adverse Events leading to Death
	Listing 16.2.7.4 Serious Adverse Events
	Listing 16.2.8.1 Clinical Laboratory: Hematology
	Listing 16.2.8.2 Clinical Laboratory: Chemistry
	Listing 16.2.8.3 Clinical Laboratory: Any Other Clinical Labs
	Listing 16.2.8.4 Vital Signs
	Listing 16.2.8.5 12-Lead ECG
Efficacy	
Figures (14.3.Y.Z)	Figure 14.3.1 Annualized Change in Estimated Glomerular Filtration Rate
	Figure 14.3.2 Annualized Percent Change from Baseline Height Adjusted Total Kidney Volume

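### Adverse events are tabulated only by SOC and single preferred term, so any-rash incidence and worst grade by cohort are not reported directly

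*SAP*

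**What the plan says.** **How adverse events will be tabulated.** SAP 3.8.1 plans that "the number and percentage of patients who experienced AEs of each specific SOC and PT will be presented". TEAEs, Grade ≥ 3 TEAEs, SAEs and TEAEs leading to dose modification or discontinuation "will be summarized by treatment arm, SOC, and PT", and the same is repeated for related events. Protocol 14.3.8 agrees: subject counts "will be tabulated by body system and preferred term both overall and by dose cohort". In SAP 4 the severity table is titled "Table 14.4.4 AEs by Preferred Term and Maximum Severity", and Table 14.4.5 (strongest relationship) is likewise by PT. Tables 14.4.6 and 14.4.7 (Grade ≥ 3, all and related) name both SOC and PT. The visible list has no rash table, grouped term or special-interest table. It does include "Listing 16.2.7.1 Adverse Events", and SAP 3.8.1 says that the listings will carry time to onset and duration.

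**How the protocol uses rash.** Protocol 5.2.2.2.3 reports of the 150 mg daily cohort: "It was noted that all 5 subjects in this cohort experienced rash within the first 28 days of treatment". It sets this beside 4 of 9 at 50 mg and 1 of 8 at 100 mg, and concludes that "this dose level was considered intolerable for long-term administration in this population". The same section reports that on 150 mg Monday and Thursday "1 subject had a severe (Grade 3) maculopapular skin rash". It then concludes that 150 mg schedules were associated with poorly tolerated rash, and that some acneiform rash occurred at 50 mg daily. Protocol 5.3.1 lists rash and acne as separate common events at 300 mg.

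**The concern.** Rash made one dose level unacceptable and counted against the 150 mg schedules. When the protocol reasons about it, the unit is a subject with rash of any kind. The SAP's unit is a subject with a given PT. If rash, acneiform rash and maculopapular rash are coded to different PTs, one toxicity is spread over several rows. The rows cannot simply be added, because a subject may appear in more than one.

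The SILK cohort of up to 50 subjects exists to describe safety at 50 mg in the population being considered for Phase 3. A reader of its tables would want to know how many subjects had any rash and how bad it became. As planned, the tables do not answer that directly. A recount done later would need a term list chosen after the data are known, in an open-label, nonrandomized study.

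**Working it through.** The plan states no figure on this point, so there is nothing to reproduce. The check has two parts.

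**1. Is there a grouped count anywhere?** The AE text in the protocol synopsis (Statistical Methods), Protocol 14.3.8 and SAP 3.8.1, and the table list in SAP 4, all stop at SOC (or body system) and PT. Rash is not among the events of special interest named in Protocol 5.3.1, which are amylase increase, pericardial effusion and QTc(F) prolongation. Some entries in the table list are redacted. They sit beside rows marked for Study 101 and appear to concern another study.

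**2. What can the planned rows say about any rash?** Let *x* be the number of subjects with any rash among *n*, spread over *k* rash PTs with row counts *x*₁ … *x*ₖ. Then

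- max(*x*ⱼ) ≤ *x* ≤ min(Σ*x*ⱼ, *n*).
- If all the rash PTs lie in one SOC, *x* ≤ that SOC row. The SOC row also holds any other event coded there. Protocol 5.2.2.1.2 and 5.2.2.2.1 report dry skin separately from rash; if it shares the SOC, the row exceeds *x*.
- Every affected subject appears in at least one row, so the largest row is at least ⌈*x*/*k*⌉. It can be as large as *x*.

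Inputs: the 28-day counts in Protocol 5.2.2.2.3. Assumption: *k* is at most 4 (rash, acneiform, maculopapular, acne). The documents do not give the coding.

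| Cohort (daily) | Any rash | Smallest possible largest row, *k* = 4 | Greatest possible largest row |
|---|---|---|---|
| 50 mg | 4/9 = 44.4% | ⌈4/4⌉ = 1, so 1/9 = 11.1% | 4/9 = 44.4% |
| 100 mg | 1/8 = 12.5% | ⌈1/4⌉ = 1, so 1/8 = 12.5% | 1/8 = 12.5% |
| 150 mg | 5/5 = 100% | ⌈5/4⌉ = 2, so 2/5 = 40% | 5/5 = 100% |

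The greatest loss is four-fold at 50 mg (4 against 1), 2.5-fold at 150 mg (5 against 2) and none at 100 mg. For 50 mg daily the protocol names only rash and acneiform rash. With *k* = 2 the smallest largest row is 2/9 = 22.2%, a two-fold loss at most.

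**Illustration at the planned size.** Assume that the 4/9 rate held in the 65 planned Phase 2a subjects on 50 mg daily: 65 × 4/9 = 28.9, so 29 subjects.

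- Any rash: 29/65 = 44.6% (95% Clopper-Pearson 32.3 to 57.5%).
- Even split over four PTs, one each: largest row ⌈29/4⌉ = 8, so 8/65 = 12.3% (5.5 to 22.8%).
- Even split over two PTs: ⌈29/2⌉ = 15, so 15/65 = 23.1%.
- All in one PT: 29/65, nothing lost.

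**The case against.** The case against a change is substantial, and much of it stands.

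- **Each PT row is correct for its own term.** A reader might infer that rash incidence is understated as a matter of fact. The documents do not support that. They give narrative descriptions, not verbatim terms or codes. Acne appears only in a list for 300 mg, a dose not used in this trial, and the maculopapular rash is one subject on 150 mg Monday and Thursday. If the events share one PT, nothing is lost.
- **The choice of 50 mg does not rest on a rash rate.** A reader might infer that it does. The 28-day counts led to an MTD of 100 mg daily (Protocol 5.2.2.2.3 and 5.4.2). The step down to 50 mg followed QTc prolongation at 100 mg (Protocol 5.2.2.2.3, 7.2.2 and 14.1). On these counts rash was more frequent at 50 mg than at 100 mg. Against Monday and Thursday dosing, 50 mg daily was preferred because of one Grade 3 rash together with dosing simplicity and the effect of missed doses.
- **There are aggregates.** A reader might infer that there are none. SAP 3.8.1 gives Grade ≥ 3 and related TEAEs a SOC level. Only Tables 14.4.4 and 14.4.5 are by PT alone in their titles.
- **A whole-study grouped row would not reproduce the protocol's counts.** Those cover 28 days, whereas treatment can run to 24 months and some 50 mg subjects could move to 100 mg. The fix therefore needs a 28-day version.
- **Safety reporting is descriptive.** No test, sample size or stopping rule depends on a pooled rash row, and the listings permit a recount.

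The last point limits the importance of the gap but does not close it. A recount from listings is not a planned result, and its term list would be chosen after the data are seen.

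**Conclusion.** The point holds as a reporting gap. Rash ruled out 150 mg daily and counted against the 150 mg schedules, and the protocol counts it per subject as one concept. No visible planned table gives any-rash incidence or maximum grade by cohort, SILK included. Single-PT rows may understate the incidence; the SOC row can only bound it from above, and only if all rash PTs share that SOC. On the protocol's own counts the understatement ranges from none to four-fold at 50 mg with up to four PTs, and to at most two-fold with the two descriptions used for that dose. Where the truth lies depends on coding that the documents do not give.

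No stated number is wrong, and nothing here calls the choice of 50 mg over 100 mg into question. This is a worthwhile and inexpensive improvement, not a flaw that threatens the trial's conclusions.

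**What to change.** In SAP 3.8.1, before database lock:

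1. Fix a list of rash PTs, agreed by a medical reviewer, and append it to the SAP.
2. Define a 'Rash (grouped)' row by cohort that counts each subject once, at maximum grade.
3. Show it in the TEAE and related-TEAE tables (14.4.2, 14.4.3), the severity and relationship tables (14.4.4, 14.4.5), the Grade ≥ 3 tables (14.4.6, 14.4.7) and the dose modification and discontinuation tables (14.4.10 to 14.4.13). Keep the individual PT rows beneath it.
4. Add a version restricted to onset in the first 28 days, so that the results can be set beside the protocol's 4/9, 1/8 and 5/5.

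The cost is one reviewed list and one derived row per table, from data already collected. The drawback is some discretion over borderline PTs such as acne; fixing the list in advance and keeping the PT rows visible contains it. No data collection, dosing or clinical rule changes.
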